**Table 34: Summary of Secondary Outcome Analysis: Steps Achieved Along a Modified SUD Cascade of Care by Treatment Arm**

Treatment Arm	Number of Participants Randomized	Results 				
		Steps Achieved at Day 180  Mean (SD)	Rate Ratio	95% Lower Confidence Limit	95% Upper Confidence Limit	p-value
TAU	N	X (X.x)	X.xx	X.xx	X.xx	0.xxx
PILOT						
Total						

 Steps achieved is collected on the following forms: HRC, SAA, MCA, DSM, UDT, and ARC

 Results are obtained from the longitudinal mixed effects model. The rate ratio and p-value result from the interaction term between treatment arm and day at Day 180.

**Table 35: Summary of Steps Achieved Along a Modified SUD Cascade of Care by Treatment Arm**

Total Number of Steps Achieved at Day 180	Treatment Arm		Total (N=XX)
	TAU (N=XX)	PILOT (N=XX)	
0	N (X.x%)		
1			
2			
3			
4			
5			
6			
7			
8			
9			
10			
Steps Achieved at Day 180			
N	X		
Mean	X.x		
SD	X.xx		
Min	X		
25 th Percentile	X.x		
Median	X.x		
75 th Percentile	X.x		
Max	X		
Number of Participants who completed each step			
1. Increase in harm reduction exposure and behaviors	N (%)		
2. Engagement in Care - Any			
3. Engagement in Care - Regular			
4. Taking MOUD – Any			
5. Taking MOUD consistently over the past 30 days			
6. Taking MOUD consistently over the past 90 days			
7. Taking MOUD consistently for 180 days			
8. Decrease SUD severity			
9. Early remission			
10. Increase in recovery capital score			

**Table 36: Summary of Potentially Eligible Patients Willing to be Engaged over Number of Approached**

Number of Potentially Eligible Patients Approached 	Number of Participants Willing to be Enrolled 	Results 		
		Proportion	95% Lower Confidence Limit	95% Upper Confidence Limit
N	N	X.x%	X.xx	X.xx

 The number of participants approached is captured on the Screening Approach (SCA) form.

 Willingness to be enrolled is defined as providing verbal consent and is captured on the ENRA or ENRY enrollment form.

 Results are obtained from the Wald confidence limits.

Table 37: Summary of Length of Engagement and Enrollment in PILOT								
Number of Participants Enrolled in PILOT	Average Length of Engagement 					Results 		
	Minimum	25 th Percentile	Median	75 th Percentile	Maximum	Mean (SD)	95% Lower Confidence Limit	95% Upper Confidence Limit
N	X.x					X.x (x.x)	X.xx	X.xx

Length of engagement is calculated from the day of randomization to the last day a PILOT participant was assessed as “engaged” or “partially engaged” on the PIL form.

 Results are obtained from the Wald confidence limits.

### 17.1.7 Supportive Analyses of the Secondary Outcome

**Table 38: Summary of Secondary Outcome Analysis: Steps Achieved Along a Modified SUD Cascade of Care by Primary Substance Use Disorder and Treatment Arm**

Primary Substance of Use 	Number of Participants Randomized	Treatment Arm		Results 			
		TAU (N =XX)	PILOT (N =XX)	Rate Ratio	95% Lower Confidence Limit	95% Upper Confidence Limit	p-value
		ORBC Score Collected at Day 180  (Mean (SD))	ORBC Score Collected at Day 180  (Mean (SD))				
Primary OUD	N	X.X (X.XX)	X.X (X.XX)	X.XX	X.XX	X.XX	0.xxx
Primary SUD other than OUD							
No SUD identified at baseline							

 Primary substance of use is identified at baseline via the DSM-5 checklist.

 Steps achieved is collected on the following forms: HRC, SAA, MCA, DSM, UDT, and ARC

 Results are obtained from the longitudinal mixed effects model. The rate ratio and p-value result from the interaction term between treatment arm, SUD subgroup, and day at Day 180.

### 17.1.8 Safety Outcomes

**Table 39: Summary of Hospitalizations by Treatment Arm**

		Treatment Arm		
Study Period 		TAU (N=XX)	PILOT (N=XX)	Total (N=XX)
Treatment Period	Number of participants with at least one hospitalization 	N (X.x%)		
	Number of participants with at least one hospitalization related to substance use 	N( X.x%)		
	Related to overdose 			
	Related to withdrawal 			
	Related to intoxication 			
	Number of hospitalizations	N	N	N
	Number of hospitalizations per participant 			
	0			
	1			
	2			
Follow-up Period	3			
	4			
	5 or more			
	Number of participants with at least one hospitalization 			
	Number of participants with at least one hospitalization related to substance use 			
	Related to overdose 			
	Related to withdrawal 			
	Related to intoxication 			
	Number of hospitalizations			
	Number of hospitalizations per participant 			
	0			
	1			
	2			
	3			
	4			
	5 or more			

Hospitalizations are as captured on the ED Visits and Hospitalization (EDH) form.

The treatment period extends from day of randomization to Study Day 180. After that, the follow-up day extends to Study Day 210.

The percentage is calculated with the denominator as the number of participants randomized.

The percentage is calculated with the denominator as the number of participants with at least one hospitalization.

The percentage is calculated with the denominator as the number of participants with at least one hospitalization related to substance use.

The hospitalization related to substance use may be due to multiple reasons.

Listing 1: Hospitalizations by Treatment Arm								
Treatment Arm = TAU								
Site	Participant ID	Date of Randomization	Hospitalization Date	Discharge Date	Primary Diagnosis/Complaint	Secondary Diagnosis/Complaint	Tertiary Diagnosis/Complaint	Outcome
xxxxx	xxxxxxxxxxxx	mm/dd/yyyy	mm/dd/yyyy	mm/dd/yyyy	xxxxxxxx	xxxxxxxx	xxxxxxxx	Recovering/resolving Recovered/resolved Recovered/ resolved with sequelae Not recovered/not resolved Fatal Unknown

Listing 1: Hospitalizations by Treatment Arm								
Treatment Arm = PILOT								
Site	Participant ID	Date of Randomization	Hospitalization Date	Discharge Date	Primary Diagnosis/Complaint	Secondary Diagnosis/Complaint	Tertiary Diagnosis/Complaint	Outcome
xxxxxx	xxxxxxxxxxxx	mm/dd/yyyy	mm/dd/yyyy	mm/dd/yyyy	xxxxxxxxxx	xxxxxxxxxx	xxxxxxxxxx	Recovering/resolving Recovered/resolved Recovered/ resolved with sequelae Not recovered/not resolved Fatal Unknown

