11.4.12 ED Visits and Hospitalizations

Data will be collected on health care utilization (inpatient and outpatient) between the index and 30-, 90-, 180-, and 210-day assessments and on an as needed basis for spontaneous reporting that occurs between study visits. ED visits and hospitalizations will be collected through self-report and review of participant electronic medical records.

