### 3.2.3 Follow-up Period

After the treatment period, participants will be followed for an additional 1-month post-intervention follow up period. The follow-up period visit and assessment are scheduled for Day 210 (7 months after randomization). This study visit window closes on Day 224.

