### 3.2.5 Safety Window

The safety window for all participants enrolled in the study begins at day of signing the IC and ends at the Day 210 follow-up visit, or after the follow-up visit window lapses for participants who do not complete this final visit, or after the site confirms that a participant is permanently done with the study (e.g., participant died or withdrew consent). Safety events will be considered treatment emergent after randomization.

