### **8.1 Hospitalizations**

Treatment period and follow-up period hospitalizations will be summarized by treatment arm. The number of participants with at least one hospitalization, number of participants with at least one hospitalization related to substance use, and number of hospitalizations per participant will be presented by treatment arm. A listing of hospitalizations by treatment arm will be generated. The listing will include Site, Participant ID, date of enrollment, date of hospitalization, discharge date, primary, secondary, and tertiary diagnosis/complaint, severity, and outcome. Hospitalizations are captured on the ED Visits and Hospitalization (EDH) form.

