### **8.2 Emergency Department Visits**

Treatment period and follow-up period ED visits will be summarized by treatment arm. The number of participants with at least one ED visit, number of participants with at least one ED visit related to substance use, and number of ED visits per participant will be presented by treatment arm. A listing of ED visits by treatment arm will be generated. The listing will include Site, Participant ID, date of enrollment, date of ED visit, discharge date, primary, secondary, and tertiary diagnosis/complaint, severity, and outcome. ED visits are captured on the ED Visits and Hospitalization (EDH) form.

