**Table 19: Summary of Treatment Exposure in PILOT Intervention: Contacts by Site and Engagement Category**

Site		Engagement Category 				Overall Engaged 
		Missing	Unengaged	Partially Engaged	Engaged	
Site 1	Number of contacts attempted 	N				
	Number of contacts attempted per participant per week					
	Mean	XX				
	SD	xx.x				
	Min	XX				
	25 th Percentile	XX				
	Median	XX				
	75 th Percentile	XX				
	Max	XX				
	Number of contacts completed 					
	Number of contacts completed per participant per week					
	Mean					
	SD					
	Min					
	25 th Percentile					
	Median					
	75 th Percentile					
	Max					
Site 2						
Site 3						
Total						

 Engagement category was assessed on the first day of the 7-day period on the Peer Intervention Log (PIL).

 Overall engaged includes partially engaged and engaged.

 Contacts attempted and completed was captured daily on the PIL.

**Table 20: Summary of Treatment Exposure in PILOT Intervention: Time Spent Engaging in Intervention Activities by Site and Intervention Period**

Site	Study Period	Missing	Time Spent Engaging in Intervention Activities 						
			No time spent (0 minutes)	1 - <15 minutes	15-30 minutes	31-45 minutes	46-60 minutes	> 1 hour	Overall 1+ minutes
Site1	Day 1 – 30	N (X.x%)	N (X.x%)	N (X.x%)	N (X.x%)	N (X.x%)	N (X.x%)	N (X.x%)	N (X.x%)
	Day 31 – 60	...							
	Day 61 – 90	...							
	Day 91 – 120								
	Day 121 – 150								
	Day 151 – 180								
	Day 181 – 210 								
	Total	...							
Site 2	...								
Site 3	...								
Total	...								

 Time spent engaging in intervention activities was captured daily on the Peer Intervention Log (PIL).

 PIL entries through the end of the follow-up visit window (Study Day 225) are included in the final intervention study period.

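### Tables 39 and 40 end follow-up at Study Day 210, so hospitalizations and ED visits collected later but still inside the safety window are left out of the by-arm counts

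*SAP*

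**What the plan says.** SAP 3.2.5 defines the safety window. For a participant who attends the last visit, it "begins at day of signing the IC and ends at the Day 210 follow-up visit". Where that visit is missed, the safety window instead stays open until the time allowed for the visit has run out. It can also end when the site establishes that participation is over for good (death and withdrawal of consent are the examples given). For the Day 210 visit, SAP 3.2.3 states: "This study visit window closes on Day 224".

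SAP 8.1 and 8.2 plan the summaries by two periods only: "Treatment period and follow-up period hospitalizations will be summarized by treatment arm" and "Treatment period and follow-up period ED visits will be summarized by treatment arm". The footnotes to the table shells give those periods their boundaries. Under Table 39, and in the same words under Table 40: "The treatment period extends from day of randomization to Study Day 180. After that, the follow-up day extends to Study Day 210".

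Collection does not stop at Day 210. Protocol 11.4.12 obtains ED visits and hospitalizations at each assessment including the 210-day one, by self-report and medical record review, and "on an as needed basis for spontaneous reporting that occurs between study visits".

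Table 20, on time spent in PILOT activities, also has a last row labelled Day 181 to 210. Its footnote says how later entries are handled: "PIL entries through the end of the follow-up visit window (Study Day 225) are included in the final intervention study period".

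**The concern.** The collection window and the reporting periods end on different days, and no rule covers the days between them. ED visits and hospitalizations are targeted safety events (SAP 3.2.6). Those that fall in the gap would be recorded on the EDH form and listed, but not counted in the only two tables that compare their frequency by arm. Table totals and listing totals could then differ with nothing in the SAP to explain why. A programmer would also have to choose between applying the footnote literally and following the safety window.

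**Working it through.** **Inputs**

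- Treatment period: randomization (Day 0, SAP 3.2.1) to Day 180; follow-up period: to Day 210 (Table 39 and 40 footnotes).
- End of safety window: actual Day 210 visit, lapse of its visit window, or site confirmation that participation is over (SAP 3.2.5).
- Close of the Day 210 visit window: Day 224 (SAP 3.2.3); Day 225 in the Table 20 footnote.
- Planned sample size: about 150.

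**Assigning days to periods under the footnotes**

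| Study day | Period in Tables 39 and 40 | Can be inside the safety window? |
|---|---|---|
| 0 to 180 | Treatment | Yes |
| 181 to 210 | Follow-up | Yes |
| 211 to 224 | None | Yes, until the visit takes place or the window lapses |

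For example, an ED visit on Day 215, reported at a Day 210 visit held on Day 218, is inside the safety window and recorded, but is counted in neither period.

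**Size of the gap**

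- Follow-up period as footnoted: 210 − 180 = 30 days.
- Follow-up period to window close: 224 − 180 = 44 days.
- Gap: 224 − 210 = 14 days.
- Share of follow-up: 14/44 = 31.8%. Share of the whole span to Day 224: 14/224 = 6.2%.
- With the Day 225 close: 15 days, 15/45 = 33.3%, and 15/225 = 6.7%.
- Seen on or before Day 210: gap = 0.

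The documents do not give the timing of Day 210 visits. Across 150 participants, the affected time therefore lies between 0 and 150 × 14 = 2,100 person-days. The upper end requires every visit to fall on Day 224 or be missed, with nobody leaving the study earlier.

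**Which outputs are affected**

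- Tables 39 and 40: yes. They are the only safety tables split by study-day period.
- Table 41 (overdoses) and Table 42 (suicide risk): no. Both are organized by visit, so a late overdose reported at the Day 210 visit is counted there.
- Listings 1 and 2 (hospitalizations, ED visits) and the death listing: no. None states a day limit.

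**The case against.** The strongest defence is that a fixed Day 181 to 210 period is sensible. The documents plan participation of up to 210 days and describe follow-up as one further month. A common cut-off gives everyone the same nominal period. Ending at the actual visit lets the length vary. If lateness differed by arm, which is possible in an open-label trial with peer outreach in one arm only, the counts could differ for reasons unrelated to safety. The safety window governs collection, and the SAP does not say that every table must span it.

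Part of this stands: varying follow-up length is a real, small cost of the fix. But the SAP does not give this reason for the cut-off, and it nowhere says that in-window events after Day 210 are to be excluded. The percentages of participants with at least one event use participants randomized as denominator, not person-time, so the cut-off is not part of an exposure adjustment. Table 20 takes the opposite approach to the same days.

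It could also be argued that Study Day 210 in the footnotes means the visit, since SAP 7.2 uses study day for the visit in the model. SAP 3.2.1 counts study days from randomization, however, and the Table 20 footnote uses the term for a calendar day. That ambiguity is itself a reason to settle the wording.

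A reader might infer three stronger things that the documents do not support:

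- **That all safety summaries stop at Day 210, or that late events are lost.** Only Tables 39 and 40 do, and Listings 1 and 2 show event date and randomization date by arm.
- **That about a third of follow-up events are missed.** The 31.8% is a share of days for one participant in the worst case. For participants who miss the visit, capture of events on Days 211 to 224 depends on spontaneous report or record review.
- **That Day 225 is wrong.** Table 20 concerns peer-log entries, and the missed-visit tables treat a visit as expected from the day after its window closes, which for this visit is Day 225. The figure may be a boundary convention.

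**Conclusion.** The point holds for two descriptive tables and is minor. On a literal reading of the footnotes, hospitalizations and ED visits after Day 210 but inside the safety window are absent from the by-arm counts in Tables 39 and 40, while remaining visible in the listings. No efficacy result is touched.

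The 14-day bound assumes a window close on Day 224 and no Day 210 visit held after that. The visit form in Protocol 11.4.2 anticipates out-of-window visits, and a later attended visit would lengthen the gap. No statement about the number of events missed, or about a difference between arms, can be made from the documents.

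**What to change.** In the footnotes to Tables 39 and 40, define the follow-up period as Day 181 to the end of the safety window in SAP 3.2.5, naming all three of its end-points. This matches what the Table 20 footnote already does for peer-log entries. Add a line under both tables saying that follow-up length varies slightly between participants. If the fixed month is in fact intended, state instead that later in-window events are excluded from these tables and shown only in Listings 1 and 2.

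Separately, reconcile the close of the Day 210 visit window between SAP 3.2.3 (Day 224) and the Table 20 footnote (Day 225). The documents do not settle which is meant.

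The cost is footnote wording and one date cut-off in the program. No new data are needed.

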**Table 40: Summary of ED Visits by Treatment Arm**

		Treatment Arm		
Study Period 		TAU (N=XX)	PILOT (N=XX)	Total (N=XX)
Treatment Period	Number of participants with at least one ED visit 	N (X.x%)		
	Number of participants with at least one ED visit related to substance use 			
	Related to overdose 			
	Related to withdrawal 			
	Related to intoxication 			
	Number of ED visits			
	Number of ED visits per participant 			
	0			
	1			
	2			
	3			
	4			
	5 or more			
Follow-up Period	Number of participants with at least one ED visit 			
	Number of participants with at least one ED visit related to substance use 			
	Related to overdose 			
	Related to withdrawal 			
	Related to intoxication 			
	Number of ED visits			
	Number of ED visits per participant 			
	0			
	1			
	2			
	3			
	4			
	5 or more			

ED Visits are as captured on the ED Visits and Hospitalization (EDH) form and do not include the index ED visit.

The treatment period extends from day of randomization to Study Day 180. After that, the follow-up day extends to Study Day 210.

The percentage is calculated with the denominator as the number of participants randomized.

The percentage is calculated with the denominator as the number of participants with at least one ED visit.

The percentage is calculated with the denominator as the number of participants with at least one ED visit related to substance use.

The ED visit related to substance use may be due to multiple reasons.

**Listing 2: ED Visits by Treatment Arm**

**Treatment Arm = TAU**

Site	Participant ID	Date of Randomization	ED Visit Date	Discharge Date	Primary Diagnosis/Complaint	Secondary Diagnosis/Complaint	Tertiary Diagnosis/Complaint	Outcome
xxxxx	xxxxxxxxxxxx	mm/dd/yyyy	mm/dd/yyyy	mm/dd/yyyy	xxxxxxxx	xxxxxxxx	xxxxxxxx	Recovering/resolving Recovered/resolved Recovered/ resolved with sequelae Not recovered/not resolved Fatal Unknown

Listing 2: ED Visits by Treatment Arm								
Treatment Arm = PILOT								
Site	Participant ID	Date of Randomization	ED Visit Date	Discharge Date	Primary Diagnosis/Complaint	Secondary Diagnosis/Complaint	Tertiary Diagnosis/Complaint	Outcome
xxxxx	xxxxxxxxxxxx	mm/dd/yyyy	mm/dd/yyyy	mm/dd/yyyy	xxxxxxxx	xxxxxxxx	xxxxxxxx	Recovering/resolving Recovered/resolved Recovered/ resolved with sequelae Not recovered/not resolved Fatal Unknown

**Table 41: Summary of Non-fatal Overdoses by Treatment Arm**

		Treatment Arm		
Visit		TAU (N=XX)	PILOT (N=XX)	Total (N=XX)
Baseline	Number of overdoses in the past 30 days	N		
	Number of participants with at least one overdose in the past 30 days	N (X%)		
	Number of overdoses per participant in the past 30 days			
	N	N		
	Mean	X.X		
	SD	X.XX		
	Min	X		
	25 th Percentile			
	Median	X		
	75 th Percentile			
	Max	X		
	Number of participants with at least one opioid overdose in the past 30 days	N (X%)		
	Number of overdoses with additional information in the past 30 days	N		
	NARCAN (naloxone) used to reverse overdose 			
	Don't know			
	No			
	Yes			
	Overdose resulting in treatment at an Emergency Department 			
	No			
	Yes			
	Overdose resulting in being admitted to the hospital 			
	No			
	Yes			
	Overdose involving opioids 			
	No			
	Yes			
	If opioid overdose, participant was trying to overdose 			
	No			
	Yes			

**Table 41: Summary of Non-fatal Overdoses by Treatment Arm**

		Treatment Arm		
Visit		TAU (N=XX)	PILOT (N=XX)	Total (N=XX)
Day 30	Number of overdoses since last study visit			
	Number of participants with at least one overdose since last study visit			
	Number of overdoses per participant since last study visit			
	N			
	Mean			
	SD			
	Min			
	25 th Percentile			
	Median			
	75 th Percentile			
	Max			
	Number of participants with at least one opioid overdose since last study visit			
	Number of overdoses with additional information during this assessment period 			
	NARCAN (naloxone) used to reverse overdose 			
	Don't know			
	No			
	Yes			
	Overdose resulting in treatment at an Emergency Department 			
	No			
	Yes			
	Overdose resulting in being admitted to the hospital 			
	No			
	Yes			
	Overdose involving opioids 			
	No			
	Yes			
	If opioid overdose, participant was trying to overdose 			
	No			
	Yes			

**Table 41: Summary of Non-fatal Overdoses by Treatment Arm**

		Treatment Arm		
Visit		TAU (N=XX)	PILOT (N=XX)	Total (N=XX)
Day 90	Number of overdoses since last study visit			
	Number of participants with at least one overdose since last study visit			
	Number of overdoses per participant since last study visit			
	N			
	Mean			
	SD			
	Min			
	25 th Percentile			
	Median			
	75 th Percentile			
	Max			
	Number of participants with at least one opioid overdose since last study visit			
	Number of overdoses with additional information during this assessment period 			
	NARCAN (naloxone) used to reverse overdose 			
	Don't know			
	No			
	Yes			
	Overdose resulting in treatment at an Emergency Department 			
	No			
	Yes			
	Overdose resulting in being admitted to the hospital 			
	No			
	Yes			
	Overdose involving opioids 			
	No			
	Yes			
	If opioid overdose, participant was trying to overdose 			
	No			
	Yes			
Day 180	Number of overdoses since last study visit			
	Number of participants with at least one overdose since last study visit			
	Number of overdoses per participant since last study visit			

**Table 41: Summary of Non-fatal Overdoses by Treatment Arm**

		Treatment Arm		
Visit		TAU (N=XX)	PILOT (N=XX)	Total (N=XX)
	N			
	Mean			
	SD			
	Min			
	25 th Percentile			
	Median			
	75 th Percentile			
	Max			
	Number of participants with at least one opioid overdose since last study visit			
	Number of overdoses with additional information during this assessment period 			
	NARCAN (naloxone) used to reverse overdose 			
	Don't know			
	No			
	Yes			
	Overdose resulting in treatment at an Emergency Department 			
	No			
	Yes			
	Overdose resulting in being admitted to the hospital 			
	No			
	Yes			
	Overdose involving opioids 			
	No			
	Yes			
	If opioid overdose, participant was trying to overdose 			
	No			
	Yes			
Day 210	Number of overdoses since last study visit			
	Number of participants with at least one overdose since last study visit			
	Number of overdoses per participant since last study visit			
	N			
	Mean			
	SD			

